APPENDIX B: DEFINITIONS AND MANAGEMENT OF INFUSION RELATED ALLERGIC REACTIONS

In the event of allergic/hypersensitivity reactions, Investigators should institute treatment measures according to best medical practice.

Any event of infusion-related reaction or allergic response, generally defined as clinically significant deviations in blood pressure, pulse, respiratory rate, and oxygen saturation, will be recorded.

In the event of infusion-related allergic reaction and if flushing, sudden rash, or difficulty breathing occur, the infusion will be stopped immediately, and affected subjects will be monitored until the infusion-related allergic reaction has resolved.

The following treatment guidelines may be employed at the discretion of the treating physician:

Grade 1 infusion-related reaction (National Cancer Institute Common Terminology Criteria for Adverse Events [NCI-CTCAE] v4.0): Mild transient reaction; infusion interruption not indicated; intervention not indicated.

Grade 2 infusion-related reaction (NCI-CTCAE v4.0): Therapy or infusion interruption indicated, but responds promptly to symptomatic treatment (e.g., antihistamines, non-steroidal anti-inflammatory drugs, narcotics, intravenous [IV] fluids); prophylactic medications indicated for ≤ 24 hours.

- 1. Decrease infusion rate by 50%, administer antihistamines, corticosteroids, etc. as medically indicated and monitor for worsening condition;
- 2. Stop infusion if infusion-related symptoms continue despite #1;
- 3. Administer bronchodilators, oxygen, antihistamines, corticosteroids etc., as medically indicated;
- 4. Resume infusion at 50% of previous rate once reaction has decreased to Grade 1 in severity. Monitor closely for any worsening; and
- 5. If the reaction reoccurs, stop infusion. Study treatment will be discontinued.

Grade 3 infusion-related reaction (NCI-CTCAE v4.0): Characterized as prolonged (e.g., not rapidly responsive to symptomatic medication and/or brief interruption of infusion); recurrence of symptoms following initial improvement; hospitalization indicated for clinical sequelae.

Grade 4 infusion-related reaction (NCI-CTCAE v4.0): Characterized as life-threatening consequences; urgent intervention indicated.

Treatment of Grade 3 or Grade 4 infusion-related reactions:

- 1. Stop the infusion immediately and disconnect infusion tubing from the subject;
- 2. Administer epinephrine, bronchodilators, antihistamines, glucocorticoids, IV fluids, vasopressor agents, oxygen, etc. as medically indicated;
- 3. Immediately contact Medpace Medical Monitor and report serious adverse event to Medpace; and
- 4. Study treatment will be discontinued.

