4.4 Enrollment Stopping Rules

An independent DSMB will meet after approximately one-third and approximately two-thirds of the subject enrollment are complete to examine unblinded safety data. See Section 9.2.4 for details about the DSMB. The stopping rules for the study include any of the following until the DSMB determines if it is safe for the study to continue enrollment:

- Serious adverse event (SAE) assessed through 3 days post-infusion that is related to investigational product; and/or
- Any Grade 3 or 4 infusion-related reaction (Common Terminology Criteria for Adverse Events v4.0) in the first 24 hours post-infusion (see Appendix B for definitions and management of Grade 2 and 4 infusion-related reactions).

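### Appendix B gives two incompatible instructions for a Grade 1 or Grade 2 allergic infusion reaction with flushing, sudden rash or difficulty breathing, and does not say which governs

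*Protocol*

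**What the plan says.** Appendix B of the Protocol opens with general text. On an infusion-related allergic reaction it says "if flushing, sudden rash, or difficulty breathing occur, the infusion will be stopped immediately", and adds that "affected subjects will be monitored until the infusion-related allergic reaction has resolved". Neither statement is tied to a severity grade.

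The graded text follows, introduced by "The following treatment guidelines may be employed at the discretion of the treating physician":

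- **Grade 1** is described as "Mild transient reaction; infusion interruption not indicated; intervention not indicated". It has no numbered steps.
- **Grade 2** is described as "Therapy or infusion interruption indicated, but responds promptly to symptomatic treatment". Step 1 is "Decrease infusion rate by 50%, administer antihistamines, corticosteroids, etc. as medically indicated and monitor for worsening condition". Step 2 stops the infusion only if symptoms persist despite step 1. Step 4 is "Resume infusion at 50% of previous rate once reaction has decreased to Grade 1 in severity".
- **Grades 3 and 4** share one set of steps, and the first is an immediate stop.

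Section 4.4 (Enrollment Stopping Rules) halts enrollment on any Grade 3 or 4 infusion-related reaction in the first 24 hours. Its cross-reference, however, reads "see Appendix B for definitions and management of Grade 2 and 4 infusion-related reactions".

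**The concern.** The general text sorts reactions by sign and the graded text sorts them by severity. A mild or moderate allergic reaction can show flushing, rash or breathing difficulty, so the two schemes overlap, and in the overlap they direct different actions on the running infusion.

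Appendix B is the Protocol's instruction for an acute event during administration of the investigational product. With 50 to 60 sites planned (Section 3.1), staff reading the same page could handle the same reaction differently, each with text to point to. That bears on patient safety. It also makes adherence hard to judge: a physician who uses the Grade 2 steps as the graded text permits would, for these signs, be departing from the mandatory sentence above them.

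**Working it through.** No figure is involved, so the check compares the texts of Appendix B.

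**Step 1: when each text applies.** The general sentence needs an infusion-related allergic reaction together with one of three signs. It sets no minimum severity. The graded text applies to infusion-related reactions by grade and makes no exception for those signs.

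**Step 2: whether the two can apply to the same event.** They can. The appendix title places all of its content, including the graded text, under allergic reactions. Grade 2 step 3 lists bronchodilators and oxygen, so the Grade 2 pathway evidently contemplates breathing symptoms. No sentence places the three signs outside Grades 1 and 2.

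**Step 3: what each directs for an allergic reaction with one of the three signs.**

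| Grade | General sentence | Graded text | Result |
|---|---|---|---|
| 1 | Stop at once | Interruption not indicated | Conflict |
| 2 | Stop at once | Step 1: halve the rate; step 2: stop only if symptoms continue | Conflict |
| 3 or 4 | Stop at once | Stop at once | Agreement |

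**Step 4: whether the document settles the conflict.** It does not. The general sentence is worded as mandatory and the graded text as optional, but neither refers to the other. The opening appeal to best medical practice does not rank them either.

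**Step 5: Section 4.4.** The trigger names Grades 3 and 4. The parenthesis sends the reader to Appendix B for Grades 2 and 4. The trigger itself is unambiguous and Appendix B covers all four grades, so this is a slip in the reference and leaves the stopping rule intact.

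**The case against.** The strongest reply is that the two texts differ in force. The stop sentence says what will be done, while the graded steps may be used at the physician's discretion, so on an ordinary reading the mandatory sentence prevails. This softens the conflict but does not remove it. The document never states that precedence, and if it is intended, Grade 2 steps 1 and 2 cannot be followed for any reaction with these signs, yet nothing at those steps says so. The discretionary block also contains mandatory wording of its own, such as the discontinuation of study treatment, so the division between the two is not clean.

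It can also be said that the Grade 1 line describes a grade and gives no order, and that the stop sentence concerns allergic reactions while the graded text speaks of infusion-related reactions more broadly. Both points have some weight. Still, a description that interruption is not indicated sits badly beside an immediate stop, and the appendix title brings the graded text under allergic reactions. The Grade 2 conflict needs no help from the Grade 1 wording.

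A reader might infer several stronger points that the document does not support:

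- **That Grade 2 contradicts itself.** Its definition calls for therapy or interruption, as alternatives. Step 1 gives therapy while slowing the rate, which satisfies it.
- **That resuming at Grade 2 step 4 conflicts with the stop sentence.** That sentence does not call the stop permanent or forbid a restart.
- **That a stopped infusion means an unrecoverable partial dose.** This fails for the same reason.
- **That the ambiguity distorts Grade 3 classification and so the enrollment halt.** Response to brief interruption is only one example in the Grade 3 description, alongside response to medication. An effect on grading is speculation.

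**Conclusion.** The conflict is real and narrow. For a Grade 1 or 2 infusion-related allergic reaction with flushing, sudden rash or difficulty breathing, Appendix B directs an immediate stop in one place. In another it describes interruption as not indicated (Grade 1), or slows the infusion first and stops it only if symptoms continue (Grade 2). No precedence is stated. Grades 3 and 4 are unaffected.

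The Grade 2 conflict is the firmer of the two, because numbered steps stand against the stop sentence. The Grade 1 conflict rests on reading the grade description as guidance for action.

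The number of subjects affected cannot be estimated from the Protocol, and no effect on the efficacy analyses is claimed. This is an inconsistency of wording that bears on patient safety and uniform conduct. The conclusion assumes that the three signs can occur in a Grade 1 or 2 reaction, which nothing in Appendix B excludes. The Section 4.4 point is a minor cross-reference error.

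**What to change.** The sponsor should reconcile the stop sentence in Appendix B with the Grade 1 wording and with Grade 2 steps 1 and 2, and state explicitly which governs when one of the three signs is present, so that each presentation has a single instruction. The choice is a clinical one for the sponsor, and this review does not say which instruction is right.

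In the same change, the grades cited in the Section 4.4 cross-reference to Appendix B should be made to match that section's own Grade 3 or 4 trigger.

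The cost is a short protocol amendment and a memo to sites. No endpoint, sample size or analysis changes.
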